Akynzeo (NEPA) is marketed as an oral fixed-dose combination of netupitant 300 mg and palonosetron 0.5 mg. Hesketh et al. conducted a double-blind randomized controlled trial in 694 patients undergoing cisplatin-based chemotherapy to examine NEPA at 3 different doses (100, 200 and 300 mg) versus palonosetron alone; an aprepitant/ondansetron group was also included in this study as an exploratory arm. The overall complete response rate (i.e. no emesis and no rescue medication 0-120 h) was 87.4%, 87.6%, 89.6%, 76.5% and 86.6%, respectively (P<0.05).²⁹ In a second study, Aapro et al. conducted a randomized controlled trial involving 1455 patients on moderately emetogenic chemotherapy. NEPA was found to be superior to palonosetron alone in achieving complete response (76.9% vs. 69.5%; P=0.001) in the delayed phase.³⁰ Gralla et al. conducted another double-blind randomized controlled safety study involving 413 patients on highly or moderately emetogenic chemotherapy..³¹ The most common adverse effects of NEPA included headache, fatigue, weakness, constipation and dyspepsia.

2016-0843 Rev. August 22, 2018 Page 5 of 22

Based on the above-mentioned studies, a recent American Society of Clinical Oncology guideline update recommended NEPA and dexamethasone as one of the options for prophylaxis of CINV among patients undergoing highly emetogenic chemotherapy regimens. Furthermore, palonosetron in combination with a corticosteroid is the preferred regimen for patients on moderately emetogenic chemotherapy.³² Of note, neither palonosetron nor NEPA have been examined in the chronic nausea and vomiting setting.

Summary of NEPA Efficacy in Clinical Trials:

In the United States, NEPA is approved for prevention of acute and delayed nausea and vomiting associated with initial and repeat courses of cancer chemotherapy, including, but not limited to, highly emetogenic chemotherapy (HEC). Various Phase 2 and Phase 3 studies conducted by Helsinn in patients with chemotherapy-induced nausea and vomiting have demonstrated that treatment with NEPA provides the following benefits:

- Shown to prevent of HEC-induced nausea and vomiting
- Increased response rate to the fixed dose combination in the prevention of CINV
- Akynzeo given 1 hour prior to chemotherapy is safe, well-tolerated, and efficacious as an antiemetic in the prevention of CINV

C. Pharmaceutical Information

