- Major protocol violation (patient lost to follow-up, hospitalization resulting from major side effects, lack of consent, lack of safety laboratory tests)
- Lost to follow-up (We will make every effort to follow all randomized patients including contact of family members and/or other medical facilities to avoid losing patients to study follow-up)
- Death
- For patients who experience an adverse event requiring cessation of study drug, they will be followed until the event resolves, until they begin another clinical trial, or until the end of the study. However, certain adverse events (e.g., a cerebrovascular accident, worsening hypertension) will not be expected to resolve completely; in these cases, the date and time should be recorded when the event reaches its new, stable equilibrium and any remaining residual of the event should be documented.
- Suspected pregnancy
- We will add replacement patients to account for withdrawals until we reach 30 total patients.

Classifications for adverse event assessment

All AEs will be assessed and documented by the investigator according to the categories detailed below.

Seriousness

For each AE, the seriousness must be determined according to the criteria given in Section F below

• Intensity

The intensity of the AE is classified according to the CTCAEv4.0. Grade refers to the severity (intensity) of the AE:

- **CTCAEv4 Grade 1**: mild; asymptomatic or mild symptoms; clinical or diagnostic observations only; intervention is not indicated.
- **CTCAEv4 Grade 2**: moderate; minimal, local, or noninvasive intervention is indicated; limiting to age-appropriate instrumental activities of daily living (ADL; instrumental ADL refers to preparing meals, shopping for groceries or clothes, using the telephone, managing money, etc).
- **CTCAEv4 Grade 3**: Severe or medically significant but not immediately life threatening; hospitalization or prolongation of hospitalization is indicated; disabling; limiting to self care ADL (self care ADL refers to bathing, dressing and undressing, feeding self, using the toilet, taking medications, and not bedridden).

CTCAEv4 Grade 4: life-threatening consequences; urgent intervention is indicated.

CTCAEv4 Grade 5: death due to an AE.

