Expected adverse events such as headache, fatigue, nausea, diarrhea, and AEs assessed as Grades 1 and 2 will not require reporting to Helsinn. Adverse events will be tracked and submitted during annual review to the IRB. Adverse events (including event name, grade, start/stop date and attribution) will be entered into Prometheus. The Principal Investigator or physician designee will verify the attribution assigned in Prometheus by signing the Prometheus adverse events printout at the end of protocol treatment. Prometheus will be utilized as the electronic case report form for this study.

Causal relationship

The assessment of the causal relationship between an AE and the administration of treatment is a clinical decision based on all available information.

The causality assessment should be done separately for each study treatment.

The assessment is based on the question whether there was a "reasonable causal relationship" to the study treatment in question.

Possible answers are "yes" or "no". An assessment of "no" would include:

1. The existence of a clear alternative explanation, e.g. mechanical bleeding at surgical site.

or

2. Non-plausibility, e.g. the subject is struck by an automobile when there is no indication that the drug caused disorientation that may have caused the event; cancer developing a few days after the first drug administration.

An assessment of "yes" indicates that there is a reasonable suspicion that the AE is associated with the use of the study treatment.

Factors to be considered in assessing the relationship of the AE to study treatment include:

- The temporal sequence from drug administration: The event should occur after the drug is given. The length of time from drug exposure to event should be evaluated in the clinical context of the event.
- Underlying, concomitant, intercurrent diseases: Each event should be evaluated in the context of the natural history and course of the disease being treated and any other disease the subject may have.
- Concomitant medication or treatment: The other drugs the subject is taking or the treatment the subject receives should be examined to determine whether any of them may be suspected to cause the event in question.
- The pharmacology and pharmacokinetics of the study treatment: The pharmacokinetic properties (absorption, distribution, metabolism and excretion) of the study treatment, coupled with the individual subject's pharmacodynamics should be considered.

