F. Investigator Communications with Helsinn

As stipulated in 2.6 of the Strategic [name] Anderson is the sponsor and assumes all obligations regarding the preparation and submission of individual and aggregate safety reports to FDA, Ethic Committee, and other relevant persons to the extent required by and as per the applicable US laws, regulations, and guidelines. The Principal Investigator will forward to Helsinn any serious adverse reaction (i.e. for which it is judged there is a reasonable causal relationship between the study drug and the adverse event) on the MedWatch Form, regardless of its expectedness, within 24 hours from first awareness, including follow-ups.

The Principal Investigator shall provide Helsinn with relevant safety data including study and IND safety reports (prior to their finalization) and any safety signal or risk (with the rationale) originating from the study. The e-mail address for exchanging all the above mentioned safety information is: [contact].

Attribution	Grade 1	Grade 2	Grade 3	Grade 4	Grade 5
Unrelated	Phase I	Phase I	Phase I	Phase I	Phase I
			Phase II	Phase II	Phase II
				Phase III	Phase III
Unlikely	Phase I	Phase I	Phase I	Phase I	Phase I
-			Phase II	Phase II	Phase II
				Phase III	Phase III
Possible	Phase I	Phase I	Phase I	Phase I	Phase I
	Phase II	Phase II	Phase II	Phase II	Phase II
		Phase III	Phase III	Phase III	Phase III
Probable	Phase I	Phase I	Phase I	Phase I	Phase I

Recommended Adverse Event Recording Guidelines

					Page 17 of 22
	Phase II	Phase II	Phase II	Phase II	Phase II
		Phase III	Phase III	Phase III	Phase III
Definitive	Phase I	Phase I	Phase I	Phase I	Phase I
	Phase II	Phase II	Phase II	Phase II	Phase II
		Phase III	Phase III	Phase III	Phase III

Adverse events will be captured according to the recommended AE recording guidelines for a Phase II protocol.

G. Serious Adverse Event Reporting

An adverse event or suspected adverse reaction is considered "serious" if, in the view of either the investigator or the sponsor, it results in any of the following outcomes:

- Death
- A life-threatening adverse drug experience any adverse experience that places the
 patient, in the view of the initial reporter, at immediate risk of death from the adverse
 experience as it occurred. It does not include an adverse experience that, had it
 occurred in a more severe form, might have caused death.
- Inpatient hospitalization or prolongation of existing hospitalization

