- Additionally, any serious adverse events that occur after the 30 day time period that are related to the study treatment must be reported to the IND Office. This may include the development of a secondary malignancy.

Reporting to FDA:

• Serious adverse events will be forwarded to FDA by the IND Sponsor (Safety Project Manager IND Office) according to 21 CFR 312.32.

It is the responsibility of the PI and the research team to ensure serious adverse events are reported according to the Code of Federal Regulations, Good Clinical Practices, the protocol guidelines, the sponsor's guidelines, and Institutional Review Board policy.

H. Statistical Considerations

The primary objective of this phase II study is to estimate the effect of NEPA on the nausea numeric rating scale (i.e. change between day 5 and day 15). The target accrual is 30 evaluable patients who complete the study with a randomization ratio of 2:1 (NEPA vs Placebo), but accrual will range from 41-50, given an attrition rate of 30-40%. With 20 patients in the NEPA arm, we would have a 92% power to detect a difference of 2 points with a standard deviation of 2.5 (effect size of 0.8) using two-sided paired t-test with a significance level of 0.05.

Descriptive statistics, including mean, standard deviation, 95% confidence intervals, median, range, frequency and percentage will be summarized for all variables of interest such as patients' demographics, clinical characteristics, personalized nausea goal, NRS and adverse effects, whichever appropriate.

We will focus on estimating the magnitude of change in NRS between day 5 and day 15. We will use a mixed model to examine the change in nausea overtime in both the NEPA arm and placebo arm.

We will estimate the proportion (with 95% confidence interval) of patients who achieve their personalized nausea goal for NEPA and placebo as a secondary outcome. Adverse effects associated with NEPA and placebo will be collected and frequency will be summarized.

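### Section F's Phase II recording rule leaves out grade 1–2 adverse events judged unrelated or unlikely, in conflict with Section E; if it governs, low-grade frequencies are understated by an unknown share

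*Combined protocol and SAP*

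**What the plan says.** Four parts of the protocol bear on which adverse events reach the analysis.

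- **Section F, Recommended Adverse Event Recording Guidelines.** Beneath a table of five attribution levels by five grades, the protocol says: "Adverse events will be captured according to the recommended AE recording guidelines for a Phase II protocol". The first line of the top row reads "Unrelated Phase I Phase I Phase I Phase I Phase I"; the Phase II label joins that row only from grade 3.
- **Section E, Classifications for adverse event assessment.** The rule is general: "All AEs will be assessed and documented by the investigator according to the categories detailed below". It continues: "Adverse events (including event name, grade, start/stop date and attribution) will be entered into Prometheus", and names that system as the electronic case report form. Its one exemption for low grades, "AEs assessed as Grades 1 and 2 will not require reporting to Helsinn", concerns what goes to the drug supplier, not what is recorded.
- **Section E, Causal relationship.** Attribution is a yes/no answer. A yes means that "there is a reasonable suspicion that the AE is associated with the use of the study treatment"; a no covers a clear alternative explanation or an implausible link.
- **Section H.** "Adverse effects associated with NEPA and placebo will be collected and frequency will be summarized". It also plans a chi-squared or Fisher's exact test on CTCAE adverse effects. This serves secondary objective 2 in Section A, which is to assess adverse effects on NEPA and on placebo.

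**The concern.** Take a grade 1 headache that the investigator thinks unlikely to be due to the capsule. Section E has it documented and entered. Section F, as the rule for capture, has it left out. Staff cannot do both, and the protocol does not say which rule yields.

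The stake is the safety description of the trial. Section B.4 reports that NEPA had not been studied in chronic nausea, and Section D.7 rests the repeat dose partly on watching adverse events closely. Section B.4 also lists the known profile: "The most common adverse effects of NEPA included headache, fatigue, weakness, constipation and dyspepsia". In patients with cancer, some of whom take opioids, such complaints may have other explanations, so attribution is a matter of opinion. If that opinion is applied before the event is recorded, the database cannot show how many events were set aside. With a randomised placebo arm, all-cause frequencies by arm can be described without any attribution.

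**Working it through.** The plan gives no figure to reproduce here, so the check is a reading of the table against the text, followed by an illustration.

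**1. Where Phase II appears in the Section F table**

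| Attribution | Grade 1 | Grade 2 | Grade 3 | Grade 4 | Grade 5 |
|---|---|---|---|---|---|
| Unrelated | no | no | yes | yes | yes |
| Unlikely | no | no | yes | yes | yes |
| Possible | yes | yes | yes | yes | yes |
| Probable | yes | yes | yes | yes | yes |
| Definitive | yes | yes | yes | yes | yes |

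Count: 3 + 3 + 5 + 5 + 5 = 21 of 25 cells; 4 are missing. The top two rows show the same pattern and the other three are complete, so the reading does not hang on a damaged cell. Section H calls the study phase II, so this is the applicable label.

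**2. Which rule governs**

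- If Section E governs, all events are in the eCRF and the table has no effect.
- If Section F governs, events in the four cells are not captured.
- If Section E is taken to mean source records and Section F the eCRF, the events survive only in source. But Section E itself sends events to the eCRF without a limit, so this reading does not remove the conflict.

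**3. Attribution scale.** The table needs five levels and Section E supplies two. The natural mapping is no for *unrelated* and *unlikely*, and yes for the other three, but the protocol does not state it. For a grade 1–2 event under Section F, the line between *unlikely* and *possible* decides whether it is recorded.

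**4. Effect on a frequency if Section F governs.** Let *p* be the true proportion of patients with a given grade 1–2 event and *s* the share of those patients whose events all fall in the omitted cells. Then

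recorded proportion = *p* × (1 − *s*).

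The arm sizes, 20 NEPA and 10 placebo, come from Section H (30 evaluable, 2:1). The documents give neither *p* nor *s*; both are assumed, with the same values in each arm.

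| Assumed *p* | *s* = 25% | *s* = 50% | *s* = 75% |
|---|---|---|---|
| 10% (2 of 20; 1 of 10) | 7.5% (1.5; 0.75) | 5% (1.0; 0.5) | 2.5% (0.5; 0.25) |
| 30% (6 of 20; 3 of 10) | 22.5% (4.5; 2.25) | 15% (3.0; 1.5) | 7.5% (1.5; 0.75) |
| 50% (10 of 20; 5 of 10) | 37.5% (7.5; 3.75) | 25% (5.0; 2.5) | 12.5% (2.5; 1.25) |

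Brackets give expected patients on NEPA and on placebo. For example, 0.30 × (1 − 0.25) = 0.225, and 0.225 × 20 = 4.5.

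Section D.7 quotes NEPA-related constipation of 3.6% and headache of 1% from an earlier trial. Those rates are already filtered by attribution, so they cannot stand in for *p*.

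**5. Effect on a contrast.** If the arms have true proportions *p*₁ and *p*₀ and share the same *s*, the recorded difference is (*p*₁ − *p*₀)(1 − *s*), while the ratio *p*₁/*p*₀ is unchanged. Absolute frequencies and differences shrink; the ratio is preserved but rests on fewer events.

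**The case against.** The best defence is that nothing need be lost. Section E is unrestricted and names the eCRF, and Section D.13 asks for attribution of all events. A reader might infer from Section F that low-grade events certainly go unrecorded. The documents do not support that; they leave open which rule applies.

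A reader might also infer that secondary objective 2 is a comparison of arms. Section A says only that adverse effects are to be assessed, and Section H says that comparing NEPA with placebo is not the study's objective. That stands. Section H nevertheless summarises frequencies for NEPA and placebo and plans association tests, so the frequencies have to mean something definite.

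A third inference is that the filter removes the very events most likely to differ between arms. This is unsupported. Every grade 1–2 event judged possible or higher is kept, and a yes needs only reasonable suspicion, which a known NEPA effect following a dose may well meet. Assessors are blinded in the randomised phase (Section D.5), so misattribution should be broadly alike in the two arms. That protects the ratio, not the absolute frequencies, and it does not extend to the open-label phase, where treatment is known.

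The wording in Sections A and H could mean attributed events only, which would fit the table. The plan does not say so; if that is meant, the tables must say it. Fatigue is also captured through the symptom scale in Table 4 regardless of attribution, but that scale does not list headache, constipation or dyspepsia among its items.

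**Conclusion.** The conflict between Sections E and F is established from the text, as is the mismatch of attribution scales. The bias is conditional: if Section F governs, each affected low-grade frequency is recorded at or below its true value, and the shortfall cannot be estimated from the eCRF. The 30% and 25–75% figures show how the mechanism works; they are assumptions and say nothing about what will happen in this trial.

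The reach is limited. Section G has all serious events reported regardless of attribution, and the table keeps all grade 3–5 events and all grade 1–2 events judged possible, probable or definitive. What is exposed is non-serious grade 1–2 events judged unrelated or unlikely. This should be corrected because it touches a stated objective and is cheap to put right. It does not threaten the primary endpoint.

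**What to change.** 1. Reconcile Sections E and F so that every adverse event of any grade is entered in the eCRF regardless of attribution. If the sponsor prefers to keep the filter, Section E must be amended to match and every frequency table must state which events it omits.
2. Use one attribution scale throughout and state how it maps to yes or no, including where *unlikely* and *possible* fall.
3. In Section H, tabulate all-cause events by arm first, by grade, with related events as a subset.
4. State the recording window for non-serious events so that it fits the dosing days in Section D.7 and the Section G window for serious events, which runs to 30 days after the last dose. A window closing at day 15 would end 4 days (96 hours) after the day 11 capsule, or 96/80 = 1.2 of the mean netupitant half-life given in Section B.4. The start also needs wording that separates the run-in capsule, to which the patient is blinded as well, from the first randomised one.

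The cost is some extra data entry for the accrual of up to 50 patients. Events filtered out before the change could be recovered only from source records, if at all, so the sooner it is made the better.

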³ T. bilirubin, albumin, prothrombin time, and serum creatinine tests can be done within 14 days of study enrollment (only if not performed in the last 14 days)

Birth Control Information

Taking part in this study can result in risks to an unborn or breastfeeding baby. Patients should not become pregnant, breastfeed a baby, or father a child while on this study. Sexually active patients must use birth control during the study.

Birth Control Specifications: Women who are able to become pregnant must use birth control during the study and for 30 days after the last NEPA dose.

Acceptable forms of birth control for men and women include barrier methods (such as condom or diaphragm) with spermicide, or abstinence.

Males must tell the doctor right away if their partner becomes pregnant or suspects pregnancy.

Pregnant women will not be enrolled on this study. If the patient becomes pregnant or suspects that she is pregnant, she must inform her doctor right away. Pregnancy may result in removal from this study.

D.3. Study screening. A 2 step consent process will be used. First, a verbal consent will be obtained by the study staff to proceed with screening of potential participants for eligibility and to characterize their nausea and vomiting. Outpatients may be contacted by phone within 1 week prior to their scheduled clinic visit to inform them of this study so they can make necessary arrangements if interested in participating. Eligible patients will then be formally enrolled onto the study after they have signed the informed consent indicating a willingness to participate in the trial. The number of patients screened, approached, eligible, and enrolled will be documented. Reasons for refusal for eligible patients will also be captured.

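### Does the lower accrual figure of 41 in Section H, which does not follow from 30% attrition, need to be changed?

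*Combined protocol and SAP*

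**What the plan says.** Section H sets the sample size by completers: "The target accrual is 30 evaluable patients who complete the study". Allocation is by a "randomization ratio of 2:1 (NEPA vs Placebo"), so 20 NEPA and 10 placebo patients among the 30. The same sentence forecasts enrolment: "accrual will range from 41-50, given an attrition rate of 30-40" per cent. It gives no inflation formula and does not explain 41.

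The power statement that follows is tied to the NEPA arm alone: "With 20 patients in the NEPA arm, we would have a 92% power". Its inputs are a 2-point difference and an SD of 2.5, hence a standardized effect of 0.8, with a paired t-test, two-sided at the 5% level.

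Two other places bear on how many patients are enrolled. Section E says: "We will add replacement patients to account for withdrawals until we reach 30 total patients". Section D.9 also replaces patients who drop out before receiving drug or placebo. Section D.1 repeats the figure of 30 evaluable patients and calls the trial a proof-of-concept study.

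**The concern.** The sentence in Section H presents the accrual range as a consequence of the attrition range, so each end should reproduce from the 30 completers and the matching attrition rate. The upper end does so exactly, which shows the rule that was used. The lower end does not, and it errs on the low side: 41 understates the enrolment needed even in the plan's most favourable case.

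If 41 were the number at which enrolment closed, the trial would expect fewer than 30 completers and fewer than 20 on NEPA. The stated power, and the precision of the estimated change in nausea score, would then be slightly optimistic.

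**Working it through.** **Inputs, all from Section H.** Target N = 30 completers; attrition d = 0.30 to 0.40; allocation 2:1; difference 2 points; SD 2.5; two-sided paired t-test at 0.05.

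**1. Upper end.** Accrual = N/(1 − d) = 30/(1 − 0.40) = 50. This matches the plan.

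**2. Lower end by the same rule.** 30/(1 − 0.30) = 42.86, rounded up to 43. The plan says 41, a gap of two patients.

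**3. The same mismatch in reverse.** Attrition that takes 41 accrued to 30 completers is 1 − 30/41 = 26.8%. Expected completers at 30% attrition:

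| Accrued | Expected completers |
|---|---|
| 41 | 41 × 0.70 = 28.7 |
| 42 | 42 × 0.70 = 29.4 |
| 43 | 43 × 0.70 = 30.1 |

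**4. Other rules that might give 41.**
- Multiplying up gives 30 × 1.30 = 39 and 30 × 1.40 = 42, which matches neither end.
- Inflating each arm at 30% gives 20/0.70 = 28.6 and 10/0.70 = 14.3. Rounded up this is 29 + 15 = 44; rounded down, 28 + 14 = 42.

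None of these gives 41.

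**5. The stated power.** Effect size 2/2.5 = 0.8. With n = 20 there are 19 degrees of freedom and the noncentrality is 0.8 × √20 = 3.58. The noncentral t distribution gives 92.4%, in agreement with the stated 92%. The accrual range does not enter this calculation.

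**6. The worst case, if 41 were a hard stop.** This sets aside the replacement rule. At 30% attrition, 28.7 × 2/3 = 19.1 NEPA completers. With n = 19 the power is 90.9%, against 92.4% with 20. The 95% confidence half-width for the NEPA change, t(0.975, n − 1) × 2.5/√n, is 1.20 points with 19 patients and 1.17 with 20.

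**7. Would 43 secure 30 completers?** Assume that losses are independent, each with probability 0.30. The chance of at least 30 completers is about 40% with 41 accrued and about 59% with 43. Neither figure secures the target in advance; the replacement rule does that.

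**The case for a change.** The best case for a correction is that this is a single division with both inputs printed in one sentence, so there is no rounding or software difference to allow for. The other end is exact, so the two ends cannot share a rule. Restating the range as 43-50 would cost one number and leave the design alone.

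The arithmetic part of this stands: 41 and 30% do not go together. The proposed remedy is less secure. The documents fit equally well with 41 being intended and 30% being a rounded form of about 27%. They do not show which figure is the slip, so 43-50 is only one of two ways to reconcile the sentence.

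A second argument is that the plan should say what attrition is counted from. Under Section D.3, "Eligible patients will then be formally enrolled onto the study after they have signed the informed consent", and under Section D.4 some of those enrolled respond to placebo in the run-in and are not randomized. Whether they count in the 30-40% would matter when the retention rates of Section D.11 are reported. It is a fair question, but a separate one. It does not explain 41, and the upper end of 50 reproduces directly when attrition is read as all loss between accrual and completion.

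**Conclusion.** The concern is right on the arithmetic, but no change follows. The lower end of a planning range is two patients below what 30% attrition implies. Correcting it would not alter the target, the conduct, the analysis, the precision or the power. Enrolment is governed by 30 completers together with replacement, and the range already extends to 50, so an enrolment of 43 lies within what was planned. Anyone who runs the trial to its stated target will pass 41 if attrition turns out to be 30%.

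The losses in step 6, 1.5 percentage points of power and 0.03 points of half-width, apply only if replacement is ignored. They are small even then and should not be read as consequences of the plan.

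This rests on two readings. The first is that the 30 patients in Section E are the same 30 evaluable completers as in Sections D.1 and H, which is the natural way to read them together. The second is that the attrition rate covers all loss from accrual to completion. The point is a clerical slip with no gain from correction.
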